Alternatively, subjects may complete the Electrocardiogram (EKG) at Medical Care San Diego ([name]) and the labs (Creatinine, BUN, electrolytes and serum pregnancy test) at either the Medical Care San Diego ([name]) or a LabCorp location close to where the subject resides. Subjects who use these facilities to complete the EKG and labs will provide the PI and his staff with the test results. Subjects will need to complete these tests no more than one week prior to the first scheduled MRI scan. The research study will pay these facilities directly on the subject's behalf with the self-pay option. Once the PI receives the test results, if he feels the results are out of range he may withdraw the subject from the study.

Study Visit 1

Location: Sharp and Children's MRI Center ([name])

The morning of the imaging procedures the subject will go to the Sharp and Children's MRI Center for the scanning procedures. The medication will need to be administered 3 hours before the start of the scan.

When the subject arrives at the MRI Center, subjects will complete a urine pregnancy test. After the pregnancy test (test must be negative), the research assistant will take the subject's blood pressure and measure her heart rate and administer the study medication. The subject will complete the Taste Labeled Magnitude Scale, Hedonic Taste Preference Scale, Food Cravings Questionnaire (State), Eating Disorders Examination (EDE-Q), Temporal Experience of Pleasure Scale (TEPS), Eating Expectancy Inventory (EEI), Beck Depression Inventory (BDI-II), The Positive and Negative Affect Schedule (PANAS), and eat a standardized breakfast.

The research staff will then review study procedures and fMRI tasks.

Subjects will then complete the fMRI and structural MRI (details of tasks outlined below).

After the scan, the research assistant will take the subject's blood pressure and heart rate and will have the subject complete the Post Scan Pleasantness Ratings and the Post MRI Questionnaire.

The total length of the study visit will be approximately 4 hours (3 hours pre-scan, 1 hour scan).

Study Visit 2

Location: Sharp and Children's MRI Center ([name])

The morning of the imaging procedures the subject will go to the Sharp and Children's MRI Center for the scanning procedures. The medication will need to be administered 3 hours before the start of the scan.

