The feasibility procedures will also include assessment of side effects from the medication. In case a study participant was to have a serious reaction (such as anaphylaxis) 911 would be called immediately and the person transported to the medical emergency room that is located about 500 yards away on campus. The study personnel are trained in basic life support.

Cardiac conduction abnormalities have been noted in individuals with anorexia nervosa. To ensure patient safety, we will only include patients in our study that are considered medically stable by the Medical Director at UC San Diego Health Eating Disorders Center for Treatment and Research (i.e. normal EKG and lab electrolyte values). If the staff at those facilities does not feel their patient is stable enough to complete the fMRI scan, the study will be postponed until she is stable, or the patient will be withdrawn from the study if timing does not allow the scan to be postponed. Study participants will have their blood pressure and heart rate taken prior to study drug administration as well as at the end of each study day. In case there is a significant drop in blood pressure indicating orthostasis during the study or due to the study medication, we will keep study participants in our research space and provide them with fluids and will recheck the blood pressure until

it has normalized. In case there were ongoing indication of orthostasis we will refer the participant to the local emergency room on campus.

Electrocardiogram. The risk is minimal. Any skin irritation from the electrode placement usually lessens within a few minutes of removing the electrode.

Data and Safety Monitoring Plan

Data will be analyzed as above for brain imaging data. The behavioral data will be analyzed using SPSS statistical software on password protected computers. The PI will perform data analysis with some research assistant support.

Subjects will be continuously monitored during their study participation by asking about how subjects feel and if they have any problems while in the study. However, in case of unexpected effects, the PI will report those to UCSD HRPP.

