25. INVESTIGATIONAL DRUG FACT SHEET AND IND/IDE HOLDER

Drug Names: Bromocriptine mesylate; Amisulpride

IND #: 191908

IND holder: [name]

[name] and the Lab Manager will be responsible for monitoring the study in the following ways:

Medication Handling and Storage

- Per 21CFR §312.6 Labeling of an investigational new drug, medications will be stored in a locked cabinet in the research office of the PI. That office is embedded in the UCSD Eating Disorder Research Program office suite, which is locked. Each study drug will be labeled with the statement “Caution: New Drug—Limited by Federal (or United States) law to investigational use.”
- Per 21CFR §312.61 Control of the investigational drug, the investigator will not supply the investigational drug to any person not authorized under this part to receive it.

Subject Level

- [name] will review all Pre-Scan Blood Test and EKG results to ensure subject's medication risks are minimized.
- Research staff will complete symptom checklist on each Study Visit day and will document the following: Documentation of blood pressure & heart rate pre-medication administration and post scan; symptom checklist including: nausea, headache, dizziness, tiredness, other. Research Staff will report these values to [name] and the Lab Manager at the end of the Study Visit.
- Research staff will contact [name] and/or Lab Manager via phone if there is a significant drop in blood pressure (20 or more points systolic) after the medication administration or significant symptoms that the subject feels keep her from continuing the study.
- [name] or Lab Manager will confirm with research team that all unexpected or adverse events (AEs/SAEs) have been reported to the IRB and FDA in the required timeframe.
- [name] or Lab Manager will review each subject folder after the subject completes the study to ensure required documentation and procedures have been completed.

Study Level

- The Lab Manager will prepare monthly aggregate reports of the adverse events, serious adverse events, and unexpected events and will review with [name].
- [name] will review monthly aggregate reports to determine safety of the study medications and whether the study is safe to be continued.

Per FDA Approval, [name] will be responsible for the following reporting requirements:

- [name] will report any unexpected fatal or life-threatening suspected adverse reactions to FDA no later than 7 calendar days after initial receipt of the information.

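### The orthostasis rule has no scheduled sitting- or lying-to-standing blood pressure behind it, so a postural fall without symptoms need not show

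*Combined protocol and SAP*

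**What the plan says.** Section 15, under challenge drug application, holds a participant on this condition: "In case there is a significant drop in blood pressure indicating orthostasis during the study or due to the study medication". She then receives fluids and repeat readings until her pressure is back to normal. The next step is "In case there were ongoing indication of orthostasis we will refer the participant to the local emergency room on campus".

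The same section schedules "blood pressure and heart rate taken prior to study drug administration as well as at the end of each study day". The visit descriptions in Section 9 agree for all three study visits and both recruitment routes: one reading just before the drug is given, and then "After the scan, the research assistant will take the subject's blood pressure and heart rate". Section 25 repeats the two time points as "Documentation of blood pressure & heart rate pre-medication administration and post scan".

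Section 25 also holds the plan's only blood pressure threshold. Staff telephone the principal investigator or the lab manager "if there is a significant drop in blood pressure (20 or more points systolic) after the medication administration", or when the participant feels that her symptoms prevent her from continuing. Symptoms are recorded each visit on a "symptom checklist including: nausea, headache, dizziness, tiredness, other".

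**The concern.** Orthostasis is a fall in pressure on standing. A rule that acts on it works best when somebody measures pressure before and after the participant stands up. The plan schedules two single readings, hours apart, in whatever posture is convenient. A participant whose resting pressure is unchanged but falls when she stands, and who reports nothing, can pass both checks and leave.

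Two features make this worth attention. Section 9 lists dizziness, faintness and fainting among bromocriptine's effects in ongoing use, although for a single dose it expects no more than nausea, headache or dizziness. Tolerability of the challenge drugs in anorexia nervosa is also a stated goal (Sections 7 and 9), in patients with a body mass index below 17.5 (Section 10). A postural response that is not measured is a piece of tolerability information that is not collected.

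**Working it through.** There is no figure in the plan to reproduce. The check is to set every scheduled blood pressure beside the rules that depend on it.

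- Section 9, Study Visits 1 to 3, both recruitment routes: one reading before the dose and one after the scan. Posture not stated.
- Section 15: one reading before the dose and one at the end of the study day. Posture not stated.
- Section 25: the same two time points. Posture not stated.
- Section 15 recheck: happens only after a fall has been found. Posture not stated.

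That gives two scheduled readings per study day, none with a stated posture, and no postural pairs.

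Next, what can Section 25's number detect? Let S0 be the pre-dose systolic pressure, S1 the post-scan systolic pressure in the same posture, and T1 the post-scan systolic pressure on standing.

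- The call rule is met when S0 − S1 ≥ 20.
- A postural fall of the same size is T1 lower than S1 by 20 or more, that is S1 − T1 ≥ 20.
- T1 is never scheduled. If S0 − S1 = 0 and S1 − T1 ≥ 20, the call rule is not met and nothing else in the scheduled readings reveals the fall.

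Because posture is free, the rule can also mislead on its own terms. If S0 is taken in one posture and S1 in another, the recorded difference is the change after dosing plus the change due to posture. The second part can hide a real fall or create an apparent one.

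Timing supports using the existing post-scan check. The drug is given 3 hours before the scan and the scan takes about 1 hour, so the check falls about 3 + 1 = 4 hours after dosing. Section 9 puts bromocriptine's plasma peak at around 3 hours, so the check comes about 1 hour after the peak.

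For scale, Section 10 plans 44 completers, each taking bromocriptine once: 44 × 1 = 44 post-bromocriptine checks. This counts occasions on which a postural fall could go unmeasured. It does not estimate how many would occur, and the documents give no rate from which to do so.

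**The case against.** A reader might infer that the hold rule has no measurable trigger at all. The documents do not support that. Section 25 uses the same phrase as Section 15 for the fall in pressure and attaches 20 systolic points to it, and the two scheduled readings suffice to apply it. On a natural joint reading, a general fall does lead to the hold and the recheck. What remains is only that a postural fall is not looked for.

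A reader might also infer that participants are left unprotected. They are not. Staff ask how participants feel, the symptom checklist includes dizziness, and Section 9 stops the study day when dizziness prevents the participant from going on. Section 15 has the principal investigator available throughout for both groups and tells examiners to stop at signs of discomfort. Patients with anorexia nervosa have further cover: a medical-stability judgement under which "the study will be postponed until she is stable", a supervised treatment setting, and sharing of adverse reactions with their program. Those three do not extend to controls recruited from the community. Most of the general measures depend on something being felt, reported or seen, so they leave the symptom-free case open.

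Finally, posture is often left to a working procedure, and Section 15 promises a detailed one before the study starts. That procedure may already specify it. If so, Section 15 need only refer to it. The documents at hand do not contain it.

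**Conclusion.** The point stands as a modest safety improvement. As written, the plan can detect a general fall of 20 systolic points from before the dose to after the scan, but it can miss a postural fall without reported symptoms, mainly after bromocriptine. This goes a little beyond missing detail, because the scheduled single readings do not match the condition that Section 15 acts on.

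The size is small and cannot be put as a number of missed events. The conclusion assumes that the two scheduled readings are single ones, as the wording suggests, and that no separate procedure already requires standing readings. No efficacy result, planned outcome or sample size is affected.

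It might seem to follow that a postural fall found before dosing should block the dose. The documents do not call for that. The postpone-or-withdraw route in Section 15 rests on program staff judging that their own patient is not stable enough, and is not written for a study reading or for controls. A new gate could also upset the 2 to 4 day spacing of scans, the one-week limit on laboratory and EKG results before the first scan, and the controls' window of the first ten days of the menstrual cycle.

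**What to change.** At the two existing time points, take blood pressure and heart rate sitting (or lying) and then standing, in the same order at every visit.

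In Section 15, state that the hold, recheck and referral steps apply after the scan to either of two findings: a postural systolic fall of a stated size (for example Section 25's 20 points, for the sponsor to confirm), or Section 25's before-after fall measured in the same posture. Do rechecks as the same pair. Report the pre-dose pair to the principal investigator as a baseline for judging the post-scan pair, not as a new condition for dosing.

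This takes a short addition to Section 15 and a matching clause in Section 25. The visit descriptions in Section 9 can stand if Section 15 governs each scheduled reading, and the technique can sit in the procedure document if Section 15 refers to it.

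The cuff, staff and time points are unchanged. Assuming 3 to 5 extra minutes at each of two time points, the cost is 2 × 3 = 6 to 2 × 5 = 10 minutes per visit, or 6/240 = 2.5% to 10/240 = 4.2% of a visit of about 240 minutes. One pair precedes the dose and the other follows the scan, so the 3-hour interval from dose to scan is kept. The other cost is an occasional longer stay, or a baseline postural fall that the principal investigator has to consider under existing discretion.

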16. PRIVACY AND CONFIDENTIALITY CONSIDERATIONS INCLUDING DATA ACCESS AND MANAGEMENT

Privacy and Confidentiality

Setting. All consenting procedures will be conducted in the private offices of the PI and research staff at the UC San Diego Health Eating Disorders Center for Treatment and Research. The Pre-Scan Study Visit will take place at ACTRI (primary option) or at San Diego Medical Care or LabCorp facilities (secondary option). Study Visit 1, Study Visit 2, and Study Visit 3 procedures will be conducted at the Sharp and Children's MRI Center.

Safeguards to Protect Subject Confidentiality. Sensitive information about a subject's medical and psychiatric history including substance abuse and treatment histories are collected as part of this research study. To protect the privacy we will keep all subject folders in locked file cabinets in the locked offices of the PI and research coordinator. Only the PI and research staff will have access to these files. In addition, the possible risk of loss of confidentiality is explained to the subject as a possible risk and he/she has the option of not participating in the study. Information about current psychiatric illness and current medication use is collected as research data. In addition, information about drug abuse and dependence is collected as part of the study. The patient populations included in this research study include participants who have been diagnosed with a medical or psychiatric condition. While this information is considered sensitive, it is necessary to collect this data to provide an accurate description of our subject populations and use as a comparison to our healthy control populations. All subjects are told in the consenting process that they can choose to not answer any question. While they do have the right to refuse to have this sensitive data collected, some of the sensitive data are necessary to collect for the outcome of the study (including substance use, medical conditions, etc.), therefore, the principal investigator may choose to withdraw or not include any participant who chooses to not have this sensitive data collected.

Data Storage and Access

When a participant enrolls in the study, a subject folder will be created that contains original documents of the ICF and HIPAA forms as well as all of the self-assessment forms and scan day forms. Payment information will also be kept in the subject folder. The folders will be kept in a locked cabinet of [name] or his research staff and access will be limited to his research staff working on this study. In addition, a subject number will be assigned to each participant and the key that contains the subject's identity will be kept electronically in a password protected file by [name] lab manager.

After the subject completes the study procedures (after Scan Day 2), the research staff will make a certified electronic copy of all of the subject's paper data which include: Signed ICF, Consent documentation, Signed HIPAA Authorization, fMRI Screening Form, Race & Ethnicity Form, Contact Information Form, Questionnaire Packet, Scan Day Assessments, Subject Face Sheet, Subject Medication Effects Log, Lab and EKG Results, and Payment information. This certified electronic copy will be stored on an encrypted and regularly backed up server at the UC San Diego Health Eating Disorders Center for Treatment and Research and access to these files will be limited to [name] and his research staff. Other electronic files to be stored on this encrypted server (de-identified): SCID 5 assessment and brain images.

The behavioral and questionnaire data will be entered into a password protected excel file. This file will contain no PHI.

The brain imaging procedures will be performed at Sharp & Children's MRI Center. This center will perform the scans as a fee for service facility and a Letter of Agreement will be established between the Department of Psychiatry at UCSD and the Sharp & Children's MRI Center. After the completion of the MRI scans, de-identified brain images will be transferred through CD or direct transfer to a landing site that will be created by the ACTRI and from there transferred to the VRD environment created for our lab by ACTRI. The data transferred will not contain PHI and access to the images will be restricted to [name] and his research staff.

Once complete, the paper documents will be securely destroyed and only the certified electronic copy and de-identified data will be kept.

All data collected under this Research Plan will be stored on the ACTRI VRD Environment created for [name] and his lab.

17. POTENTIAL BENEFITS

There is no direct benefit for individuals participating in this study. However, individuals with AN participating in this study may benefit from the screening procedures that include a careful examination of the subject's psychiatric condition. They may request a copy of the in-depth diagnostic assessment that they may share with their provider if they wish or review with the PI.

18. RISK/BENEFIT RATIO

Risk/Benefit Ratio: This study involves questionnaires, in person assessments, a blood draw, EKG and 3 fMRI scans with administering a single dose of 2 medications and placebo to subjects and there are potential risks to taking the medication as outlined above. Anorexia nervosa (AN) is the most deadly disease among the psychiatric disorders ([Sullivan, 1995](#)) and no medication has been approved to this date to treat the disorder. There is a potential benefit of investigating the concept that direct receptor acting medication can ameliorate excessive brain dopamine related reward response in AN and thus could in fact become an important treatment for this disorder; therefore, we feel the potential benefits outweigh the risks involved in this pilot study.

Importance of the knowledge to be gained

The results from this project will

(1) provide information on how feasible brain imaging and dopamine challenge drug application is in anorexia nervosa.

(2) provide important new information on how dopamine D2 receptors are involved in prediction error response and reversal learning within anorexia nervosa and healthy control groups.
(3) provide pilot data whether healthy controls or individuals with anorexia nervosa can be distinguished by dopamine receptor-driven brain response.

Anorexia Nervosa has the highest mortality rate among the psychiatric disorders and is associated with an immense amount of suffering for the patients and their families. The results of this study will help us identify how dopamine receptor function is involved in altered brain activation and behavior response in anorexia nervosa. What this may help is identify targets for pharmacological intervention. We believe that the benefits of the study by far outweigh the potential risks.

19. EXPENSE TO PARTICIPANT

None

20. COMPENSATION FOR PARTICIPATION

Questionnaire Packet & Initial Screenings: \$25

Diagnostic Assessment: \$25

Pre-Scan Study Visit: \$25

Study Visit 1, 2, 3: \$150/Study Visit

Reimbursement for Parking at ACTRI Pre-Scan Visit: \$5

Total Compensation for Study: \$530

Although rare, it is possible that the MR scanner may have errors or problems or there are personnel issues, or problems with the taste pump, etc. that prevent us from completing the scheduled study visit day. Sometimes these issues are not known until the start of the scan after the subject has already completed many of the questionnaires, taste test, etc. If the timing of the scan allows us to reschedule one/both of the Study Visits, we will ask the subject if they are willing to come back to complete an additional study visit day and will compensate them \$100 for the incomplete study visit in addition to the amount they receive for the regular study procedures.

Ineligible subjects or subjects who withdraw from the study prior to Study Visit 1 will receive an electronic gift card in the amount of \$25, \$50 or \$75 (depending on what stage of the study the subject completed) to Amazon or Target.

In the consent form the subject is informed that compensation in this study is considered taxable income and after the subject passes the Screening Visit, the subject will be given instructions on how to register herself on Payment Compass. The subject will be reminded that research staff will submit a request for payment to UCSD after they complete the study and that if they are excluded or withdraw prior to the first MRI scan (Study Visit 1), they will be compensated in the form of an electronic gift card.

If a subject did not choose to register herself on Payment Compass (or those individuals who do not have easy access to complete the Self-Registration process on Payment Compass, such as AN subject in a treatment program with limited internet access), we will have the subject complete a paper W9 form with their social security number and contact information. The research staff will then register the subject in Payment Compass and submit the payment request to UCSD after the completion of the study.

The payment is to serve as an incentive for subject participation and to reimburse travel, study time and expenses. Although the individual subject may not receive any benefit beyond financial remuneration, the data

generated by this project could significantly enhance our knowledge about altered brain function with respect to anorexia nervosa and pave the way for new clinical measures and treatments for those disorders.

